15. PROTOCOL AMENDMENTS

The sponsor may not implement a change in the design of the protocol or ICF without an IRB- or EC-approved amendment. All substantial protocol amendments will be approved by the competent authorities before changes are implemented according to national regulations.

16. PREMATURE TERMINATION OF THE STUDY OR CLOSE-OUT OF A SITE

16.1. Premature Termination of the Study

The sponsor has the right to terminate the study prematurely. Reasons may include efficacy, safety, or futility, among others. Should the sponsor decide to terminate the study, the investigator(s) will be notified in writing.

16.2. Close-out of a Site

The sponsor and the investigator have the right to close-out a site prematurely.

Investigator's Decision

The investigator must notify the sponsor of a desire to close-out a site in writing, providing at least 30 days' notice. The final decision should be made through mutual agreement with the sponsor. Both parties will arrange the close-out procedures after review and consultation.

Sponsor's Decision

The sponsor will notify the investigator(s) of a decision to close-out a study site in writing. Reasons may include the following, among others:

- The investigator has received all items and information necessary to perform the study, but has not enrolled any patient within a reasonable period of time
- The investigator has violated any fundamental obligation in the study agreement, including but not limited to, breach of this protocol (and any applicable amendments), breach of the applicable laws and regulations, or breach of any applicable ICH guidelines
- The total number of patients required for the study are enrolled earlier than expected

In all cases, the appropriate IRB or EC and Health Authorities must be informed according to applicable regulatory requirements, and adequate consideration must be given to the protection of the patients' interests.

17. STUDY DOCUMENTATION

17.1. Certification of Accuracy of Data

A declaration assuring the accuracy and content of the data recorded on the eCRF must be signed electronically by the investigator. This signed declaration accompanies each set of patient final eCRF that will be provided to the sponsor.

17.2. Retention of Records

The investigator must retain all essential study documents, including ICFs/IAFs, source documents, investigator copies of CRFs, and drug accountability records for at least 15 years following the completion or discontinuation of the study, or longer, if a longer period is required by relevant regulatory authorities. The investigator must obtain written approval from the sponsor before discarding or destroying any essential study documents during the retention period following study completion or discontinuation. Records must be destroyed in a manner that ensures confidentiality.

If the investigator's personal situation is such that archiving can no longer be ensured, the investigator must inform the sponsor (written notification) and the relevant records will be transferred to a mutually agreed-upon destination.

18. DATA QUALITY ASSURANCE

In accordance with ICH E6, the sponsor is responsible for quality assurance to ensure that the study is conducted and the data generated, recorded, and reported in compliance with the protocol, GCP, and any applicable regulatory requirement(s). The planned quality assurance and quality control procedures for the study are summarized.

Data Management

The sponsor is responsible for the data management of this study including quality checking of the data (Section 11.1).

Study Monitoring

The investigator must allow study-related monitoring, IRB/EC review, audits, and inspections from relevant health regulatory authorities, and provide direct access to source data documents (Section 12.1, Section 12.2, and Section 13)

The study monitors will perform ongoing source data review to verify that data recorded in the CRF by authorized site personnel are accurate, complete, and verifiable from source documents, that the safety and rights of patients are being protected, and that the study is being conducted in accordance with the current approved protocol version and any other study agreements, ICH GCP, and all applicable regulatory requirements (Section 12.1).

All subject/patient data collected during the study will be recorded on paper or electronic CRF unless the data are transmitted to the sponsor or designee electronically (eg, laboratory data). The investigator is responsible for affirming that data entries in the CRF are accurate and correct by electronically signing a declaration that accompanies each set of patient/subject final CRF (Section 12.3 and Section 17.1).

Study Documentation

The investigator must maintain accurate documentation (source data) that supports the information entered in the CRF (Section 12.2).

The investigator will retain all records and documents, including signed ICFs, pertaining to the conduct of this study for at least 15 years after study completion, unless local regulations or institutional policies require a longer retention period. No records may be destroyed during the retention period without the written approval of the sponsor. No records may be transferred to another location or party without written notification to the sponsor (Section 17.2).

19. CONFIDENTIALITY

Confidentiality of information is provided as a separate agreement.

20. FINANCING AND INSURANCE

Financing and insurance information is provided as a separate agreement.

21. PUBLICATION POLICY

Publication rights and procedures will be outlined in a separate clinical study agreement.

## LIST OF ABBREVIATIONS AND DEFINITION OF TERMS

Ab	Antibody
ACQ-5	Asthma Control Questionnaire-5
AD	Atopic dermatitis
ADA	Anti-drug antibody
AE	Adverse event
AESI	Adverse event of special interest
ALT	Alanine aminotransferase
ANCOVA	Analysis of covariance
AST	Aspartate aminotransferase
BID	Twice (two times) a day
BUN	Blood urea nitrogen
CMH	Cochran-Mantel-Haenszel (test)
CPK	Creatine phosphokinase
CRF	Case report form
CRO	Contract research organization
CSR	Clinical study report
C trough	Trough concentration
DMC	Data monitoring committee
DSQ	Dysphagia Symptom Questionnaire
EC	Ethics committee
ECG	Electrocardiogram
eCRF	Electronic case report form
eCOA	Electronic clinical outcome assessment
EDC	Electronic data capture
eGFR	Estimated glomerular filtration rate
EndoFLIP	Endolumenal functional lumen imaging probe
EoE	Eosinophilic esophagitis
EoE-EREFS	Eosinophilic Esophagitis-Endoscopic Reference Score
EoEHSS	EoE Histology Scoring System
EoE-IQ	EoE Impact Questionnaire
EoE-SQ	EoE Symptom Questionnaire
EOS	End of study (visit)
eos/hpf	Eosinophils/high power field
EOT	End of treatment
EQ-5D	European Quality of Life 5-Dimensional Scale

ET	Early termination
FAS	Full analysis set
FSH	Follicle stimulating hormone
HBcAb	Hepatitis B core antibody
HBsAb	Hepatitis B surface antibody
HBsAg	Hepatitis B surface antigen
HCV	Hepatitis C virus
HDL	High-density lipoprotein
HIV	Human immunodeficiency virus
IA	Interim analysis
IAF	Informed assent form
ICF	Informed consent form
ICH	International Council for Harmonisation
IgE	Immunoglobulin E
IgG4	Immunoglobulin G4
IL	Interleukin
IL-4R $\alpha$	Interleukin-4 receptor alpha
ISR	Injection site reaction
IWRS	Interactive voice/web response system
LDH	Lactate dehydrogenase
LDL	Low-density lipoprotein
LOCF	Last observation carried forward
MedDRA	Medical Dictionary for Regulatory Activities
MMRM	Mixed-effect model repeated measure
NAb	Neutralizing antibody
OIT	Oral immunotherapy
PCSV	Potentially clinically significant value
PGIC	Patient Global Impression of Change of Dysphagia
PGIS	Patient Global Impression of Severity of Dysphagia
PK	Pharmacokinetic
POEM	Patient-Oriented Eczema Measure
PPI	Proton pump inhibitor
PRO	Patient-reported outcome
PT	Preferred term (MedDRA)
QOL	Quality of life

Q2W	Once every two weeks
QW	Once weekly
RBC	Red blood cell
RQLQ(s)+12	Rhinoconjunctivitis Quality of Life Questionnaires for 12 years and older
SAE	Serious adverse event
SAF	Safety analysis set
SAP	Statistical analysis plan
SAS	Statistical Analysis Software
SC	Subcutaneous
SD	Standard deviation
SLIT	Sublingual immunotherapy
SOC	System organ class
STC	Swallowed topical corticosteroids
TARC	Thymus and activation-regulated chemokine
TB	Tuberculosis
TEAE	Treatment-emergent adverse event
Th2	Type 2 helper T cell
TNSS	Total Nasal Symptom Score
ULN	Upper limit of normal
WBC	White blood cell
WOCF	Worst observation carried forward

## 1. OVERVIEW

The purpose of the statistical analysis plan (SAP) is to ensure the credibility of the study results by pre-specifying the statistical approaches for the analysis of study data prior to database lock. The SAP is intended to be a comprehensive and detailed description of the strategy and statistical methods to be used in the analysis of data for R668-EE-1774 study Part B, as well as Part B patients' data in Part C as extended active treatment and in the 12-week follow-up period. A separate Part A SAP was finalized on 21 April 2020 for the analysis of data from Part A, and Part A patients' data in Part C and 12-week follow-up period before Part A DBL.

This plan will be finalized prior to the data lock for the end of Part B, i.e., the last Part B patient reaching week 24 visit.

### 1.1. Background/Rationale

Eosinophilic esophagitis (EoE) is a chronic, inflammatory, allergic/immune-mediated disease of the esophagus. The disease is characterized by local eosinophilic inflammation leading to symptoms of esophageal dysfunction. The primary clinical manifestations of EoE in both adults and adolescents are dysphagia and food impaction ([Hudgens, 2017](#)). Growing evidence suggests that a type 2 cytokine-mediated immune response plays an important role in the pathogenesis of EoE. The inflammatory damage to the esophageal epithelium results in symptoms of esophageal dysfunction, such as dysphagia. Chronic inflammation of the esophagus may also lead to remodeling, stricture formation, and fibrosis.

Current therapeutic approaches include high dose proton pump inhibitors, dietary modification with specific food elimination, swallowed topical corticosteroids (not approved for the treatment of EoE in adolescents or in adults outside the European Union [EU]), and esophageal dilation when esophageal narrowing/or strictures develop. The therapies for eosinophilic esophagitis are limited by variable response rates, relapse after therapy cessation, and adverse effects on quality of life. High dose proton pump inhibitors lead to histologic remission in approximately half of the patients ([Lucendo, 2016](#)). Swallowed topical corticosteroids have shown variable response, and maintainance of compliance is challenging due to the potential risks of side effects. Endoscopic dilation for prolonged and/or painful food impaction is an emergency procedure utilized for symptomatic relief if the patient cannot pass the food or induce vomiting. It is associated with a risk of severe esophageal injury and does not alter the underlying pathogenesis or progression of the disease. As such, there is a significant unmet need for new treatments across the age spectrum targeting key pathways driving the inflammation in EoE ([Rothenberg, 2015](#), [Spergel, 2012](#), [Greuter, 2017](#)).

Dupilumab is a human monoclonal immunoglobulin G4 (IgG4) antibody (Ab) that inhibits IL-4 and IL-13 signaling by specifically binding to the IL-4 receptor alpha (IL-4R $\alpha$ ) subunit shared by the IL-4 and IL-13 receptor complexes. Blocking IL-4R $\alpha$  with dupilumab inhibits IL-4 and IL-13 cytokine-induced responses, including the release of pro-inflammatory cytokines, chemokines, and IgE. Additionally, preclinical data demonstrate that treatment with dupilumab prevents infiltration of eosinophils into tissues. For these reasons, dupilumab was evaluated in adult patients with EoE in a phase 2, multicenter, double-blind, randomized, placebo-controlled study (R668-EE-1324), where it demonstrated substantial improvements in clinical (based on the Straumann Dysphagia Instrument), histologic, and endoscopic aspects of the disease. Dupilumab was well

tolerated in the study, with safety data generally consistent with other dupilumab studies in patients with AD, in patients with asthma, and patients with chronic rhinosinusitis with nasal polyps. No new safety signal associated with dupilumab use was identified in the EoE patient population. The results from phase 2 support the phase 3 evaluation of dupilumab in EoE.

Additional background information on the study drug and development program can be found in the most recent Investigator's Brochure.

This phase 3 study was to investigate the efficacy and safety of dupilumab in adult and adolescent patients with EoE in a 3-part study. Part A and Part B are 24-week treatment, randomized, double-blind, placebo-controlled studies. In Part A, patients were randomized to receive dupilumab 300 mg QW or placebo; In Part B, patients were to be randomized to receive dupilumab 300 mg Q2W, dupilumab 300 mg QW, or placebo. Patients who had participated in Part A would not be eligible to participate in Part B. At the end of Part A, eligible patients were offered an option to enter Part C for an extended treatment period to receive dupilumab 300 mg QW. At the end of Part B, eligible patients were to be provided with an option to enter Part C to receive dupilumab 300 mg Q2W or dupilumab 300 mg QW in a blinded fashion for an additional 28 weeks. Patients in Parts A/B who not entering Part C would enter a 12-week post-treatment follow-up period immediately after Part A/B.

## **1.2. Study Objectives**

### **1.2.1. Primary Objectives**

#### **Parts A and B**

To demonstrate the efficacy of dupilumab treatment compared with placebo in adult and adolescent patients with EoE after 24 weeks of treatment as assessed by histological and clinical measures.

#### **Part C**

To assess the safety and efficacy of dupilumab treatment in adult and adolescent patients with EoE after up to 52 weeks of treatment as assessed by histological and clinical measures.

### 1.2.2. Secondary Objectives

The secondary objectives of the study are:

- To evaluate the safety, tolerability, and immunogenicity of dupilumab treatment for up to 52 weeks in adult and adolescent patients with EoE
- To explore the relationship between dupilumab concentration and responses in adult and adolescent patients with EoE, using descriptive analyses
- To evaluate the molecular effects of dupilumab on transcriptomic signatures associated with EoE and type 2 inflammation
- To demonstrate the efficacy of dupilumab treatment compared with placebo after 24 weeks and 52 weeks of treatment in adult and adolescent patients with EoE who have previously received swallowed topical corticosteroids

### 1.2.3. Modifications from the Statistical Section in the Final Protocol

The Part B per protocol analysis set (PPS) is removed since estimands are constructed, with aligned method of analysis, that better address the objective and analysis of PPS might not add additional insights.

### 1.2.4. Revision History for SAP Amendments

The purpose of this SAP amendment is to

- (1) add analyses per feedback received from a Health Authority
- (2) clarify the analysis of EoE-EREFS and update the hierarchical testing order before database lock.

Description of Change	Rationale	Section Changed
To add 2 supplemental analyses for co-primary endpoint of absolute change in DSQ score from baseline to week 24	As per Health Authority recommendation	Section 5.6.1 Analysis of Co-Primary Efficacy Variable(s)
To add DSQ-related analyses	As per Health Authority recommendation	Section 4.4.3 Exploratory Efficacy Variable (s) Section 5.6.5 Analysis of Exploratory Efficacy Variables
To update the hierarchical testing order	To address a Health Authority recommendation	Section 5.6.3 Adjustment for Multiple Comparison
To clarify the analysis of EoE-EREFS	To be consistent in the analysis between Part A and Part B and to be in line with the intent of the protocol to utilize investigator assessed EoE-EREFS data for the analysis if the images for central reading are not available (e.g. due to	Section 4.4.2 Secondary Efficacy Variable(s) Section 5.6.2 Analysis of Secondary Efficacy Variables

	technical and image quality issues)	
Editorial changes	To clarify that the the analysis of psychometric validity of patient reported outcome measures is described in a separate Psychometric Analysis Plan	Section 5.12 Analysis of Psychometric Validity of Patient Reported Outcome Measures
	To clarify that the Part B CSR will be written separated from the Part B patients' Part C CSR	Section 8 Timing of Statistical Analysis

## 2. INVESTIGATION PLAN

[figure not shown]
### 2.1. Study Design and Randomization

Part B is a 24-week treatment, randomized, double-blind, placebo-controlled study phase to determine the treatment effect of dupilumab compared with placebo in adult and adolescent patients with EoE as assessed by histological and clinical measures. After a screening period up to 12 weeks, patients were centrally randomized via interactive web response system (IWRS) in a 1:1:1 ratio to dupilumab 300 mg SC QW, dupilumab 300 mg SC Q2W or placebo SC and treated double-blind for 24 weeks in Part B. Randomization was stratified by age ( $\geq 18$  vs.  $\geq 12$  to  $< 18$  years of age) and use of PPI at randomization (yes vs. no). At the end of Part B, eligible patients were to be provided an option to enter Part C, which consists of a 28-week period of active treatment with dupilumab. Patients from Part B who were randomized to placebo during the double-blind treatment period would be re-randomized in a 1:1 ratio to dupilumab 300 mg QW or dupilumab 300 mg Q2W. Patients from Part B who were randomized to dupilumab during the double-blind treatment period would remain on the same dupilumab treatment in Part C. Treatment assignment in Part C were managed by an interactive web response system (IWRS) to maintain blinding of treatment assignment in Part B. All patients would be followed up for an additional 12 weeks after completing Part C. Patients in Part B who do not enter Part C would enter a 12-week follow-up period immediately after Part B. Patients who participated in Part A were not eligible to participate in Part B.

Approximately 210 patients (70 per treatment group) are planned to be randomized in Part B from multiple global sites.

The design of the overall study is depicted below in [Figure 1](#). As Part A and Part B are carried out as 2 separate sub-studies with no overlap in patients, Part A and Part B will each have a separate 2-sided alpha level of 0.05.

**Figure 1: Overall Study Design**

## 2.2. Statistical Hypothesis

For the comparison of each of the 2 dupilumab treatment groups to placebo, the following hypotheses of the co-primary endpoints will be tested, where  $p_d$  is the true proportion of patients achieving peak esophageal intraepithelial eosinophil count of  $\leq 6$  eos/hpf at week 24 and  $\mu_d$  is the true mean change from baseline in the DSQ total score at week 24 in the dupilumab group; and  $p_p$  and  $\mu_p$  are the corresponding true values in the placebo group.

- Proportion of patients achieving peak esophageal intraepithelial eosinophil count of  $\leq 6$  eos/hpf at week 24
  - Null hypothesis ( $H_0$ ):  $p_p = p_d$ , ie, the proportion of patients achieving peak esophageal intraepithelial eosinophil count of  $\leq 6$  eos/hpf at week 24 is the same between the dupilumab group and the placebo group.
  - Alternative hypothesis ( $H_1$ ):  $p_p \neq p_d$ , ie, the proportion of patients achieving peak esophageal intraepithelial eosinophil count of  $\leq 6$  eos/hpf at week 24 is different between the dupilumab group and the placebo group.
- Change from baseline in the DSQ total score at week 24
  - Null hypothesis ( $H_0$ ):  $\mu_p = \mu_d$ , ie, the mean change from baseline in the DSQ total score at week 24 is the same between the dupilumab group and the placebo group.
  - Alternative hypothesis ( $H_1$ ):  $\mu_p \neq \mu_d$ , ie, the mean change from baseline in the DSQ total score at week 24 is different between the dupilumab group and the placebo group.

### 2.3. Sample Size and Power Considerations

Efficacy assessment employs the following co-primary endpoints measuring histologic and clinical symptoms of disease, respectively:

- Proportion of patients achieving peak esophageal intraepithelial eosinophil count of  $\leq 6$  eos/hpf at week 24
- Absolute change in Dysphagia Symptom Questionnaire (DSQ) score from baseline to week 24

The assumptions used in sample size calculations are based on results from Part A of the study as below:

- The proportion of patients achieving peak esophageal intraepithelial eosinophil count of  $\leq 6$  eos/hpf at 24 weeks was 5.1% in placebo group and 59.5% in dupilumab 300mg QW group with a treatment difference of 55.4%
- The mean (standard deviation [SD]) of change from baseline in DSQ total score at week 24 was -9.6 (15.2) in placebo and -21.9 (14.6) in the dupilumab 300mg QW group with a treatment group difference of -12.3.

Based on the Part A study results, the planned sample size for Part B is approximately 70 patients in each treatment group such that for the comparison of each dupilumab treatment group to placebo:

- This sample size will yield >99.9% power to detect a treatment difference of 55.4% in the proportion of patients achieving peak esophageal intraepithelial eosinophil count of  $\leq 6$  eos/hpf at week 24 between placebo (5.1%) and each dupilumab treatment group (59.5%) at a 2-sided significant level of 5% using Fisher's exact test.
- This sample size will provide >99.9% power to detect a treatment difference of -12.3 points in the mean change from baseline in the total DSQ score to week 24 at a 2-sided significance level of 5% using a two-sample t-test, assuming a common SD of 15.0.

Therefore, the sample size of 70 patients/arm will provide an overall power of >99.9% (99.9%  $\times$  99.9%) for the co-primary endpoints, assuming no negative correlation between the two endpoints. In Part B, the same treatment effect for the two 300 mg dupilumab dose regimens (ie, QW and Q2W) is assumed.

A dropout rate of 15% is assumed for the sample size calculations.

[figure not shown]
Sample size calculations were made using nQuery Advisor 7.0.

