- For all endoscopies, the investigators will assess minor esophageal features including mucosal inflammatory and remodeling features. DSQ will be completed daily by patients in the eDiary to assess the frequency and severity of dysphagia.
- The EoE-IQ, a disease-specific measure of health-related QOL in EoE patients, will be completed by patients at specified time points.
- The EoE Symptom Questionnaire, a questionnaire measuring the frequency and severity of symptoms other than dysphagia and swallowing pain, will be completed by patients at specified time points.
- The endolumenal functional lumen imaging probe (EndoFLIP) procedure to measure esophageal distensibility may be performed during the esophagogastroscope procedures at selected North American sites in approximately 150 adult patients.

Safety and tolerability will be assessed by physical examinations, vital signs, electrocardiograms (ECGs), clinical laboratory tests, and clinical evaluations. Patients will be asked to report all adverse events (AEs) experienced from the time of informed consent until their last study visit.

Pharmacokinetics (PK): Serum samples will be collected at specified time points for assay of dupilumab concentration.

Anti-drug antibody (ADA): Serum samples will be collected at specified time points for assay of ADA and exploratory analyses.

Statistical Plan

Sample Size

Part A: The planned sample size for Part A is approximately 40 patients in each treatment group.

Part B: Based on the Part A study results, the planned sample size for Part B is approximately 70 patients in each treatment group such that for the comparison of each dupilumab dose regimen to placebo:

- This sample size will yield >99.9% power to detect a treatment difference of 55.4% in the proportion of patients achieving peak esophageal intraepithelial eosinophil count ≤ 6 eos/hpf at week 24 between placebo (5.1%) and the dupilumab treatment group (59.5%) at a 2-sided significance level of 5% using Fisher's exact test.
-

- This sample size will provide >99.9% power to detect a treatment difference of -12.3 points in the mean change from baseline in the total DSQ score to week 24 at a 2-sided significance level of 5% using a two-sample t-test, assuming a common standard deviation (SD) of 15.043.0.

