Therefore, the sample size of 70 patients/arm will provide an overall power of >99.9% (99.9% × 99.9%) for the co-primary endpoints, assuming no negative correlation between the two endpoints. In Part B, the same treatment effect for the two 300 mg dupilumab dose regimens (ie, QW and Q2W) is assumed.

Efficacy Analysis Sets

For Part A and Part B, the efficacy endpoints will be analyzed using the study-part-specific full analysis set (FAS) that includes all randomized patients in the corresponding study part.

The efficacy endpoints in Part C (the extended active treatment period) will be summarized for all patients who received any extended active treatment study drug in that part.

Safety Analysis Set

For Part A and Part B, the study-part-specific safety analysis set (SAF) includes all randomized patients who received any study drug in the corresponding study part; it is based on the treatment received (as treated). Treatment compliance/administration and all clinical safety variables will be analyzed using the SAF.

For safety analyses of the Part C extended treatment period, only a subset of SAF will be included, which is defined as those patients who received at least 1 dose of Part C study drug.

Statistical Analysis

All statistical analyses will be conducted separately for Part A and Part B.

Primary Efficacy Analysis (Part A and Part B):

The co-primary endpoint of proportion of patients achieving a histologic response of peak esophageal intraepithelial eosinophil count ≤6 eos/hpf at week 24 will be analyzed using the Cochran-Mantel-Haenszel (CMH) test to assess the difference in the proportion of responders in the FAS, adjusting for the randomization stratification factors.

The co-primary endpoint of absolute change from baseline in the DSQ total score at week 24 will be analyzed using an analysis of covariance (ANCOVA) model for the FAS with treatment group, randomization stratification factor, and relevant baseline measurement as covariates included in the model.

To account for use of rescue treatment in the primary analysis, for peak esophageal intraepithelial eosinophil count of ≤6 eos/hpf, patients will be considered as non-responders after the use of rescue treatment. For absolute change from baseline in the DSQ total score, data will be imputed using multiple imputation (MI) for all time points subsequent to the use of rescue treatment.

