10.2. Justification of Sample Size

The assumptions used in sample size calculations for Part A are based on results from a phase 2 study of dupilumab (R668-EE-1324) and reported data of a phase 2 study of budesonide (Dellon, 2017) in patients with EoE as follows:

- In the study of dupilumab, a treatment difference of 65.2% was observed in the proportion of patients achieving peak esophageal intraepithelial eosinophil count of ≤ 6 eos/hpf after 12 weeks of treatment (placebo 0% vs. dupilumab 65.2%). DSQ was not assessed in this study. The overall dropout rate was 8.5% during the 12-week treatment period.

- In the study of budesonide oral suspension, a treatment difference of 36% was observed in the proportion of patients achieving peak esophageal intraepithelial eosinophil count of ≤ 6 eos/hpf after 12 weeks of treatment (placebo 3% vs. budesonide 39%). The mean (standard deviation [SD]) of change from baseline in DSQ total score at week 12 was -7.5 (10.7) in placebo and -14.3 (13.0) in the budesonide group, corresponding to a treatment group difference of -6.8. The overall dropout rate was 6.5% during the 12-week treatment period.

With the consideration that a higher dropout rate may be observed for a longer treatment period, a dropout rate of 15% is assumed for all sample size calculations provided below.

Part A

The planned sample size for Part A is approximately 40 patients in each treatment group such that for the comparison of each dupilumab dose regimen to placebo:

- This sample size will yield >99% power to detect a treatment difference of 62% in the proportion of patients achieving peak esophageal intraepithelial eosinophil count of ≤ 6 eos/hpf at week 24 (placebo 3% vs. dupilumab 65%) at a 2-sided significance level of 5% using Fisher's exact test.
- With respect to the treatment group difference in the mean change from baseline in DSQ total score, assuming a common SD of 13.0, this sample size is expected to generate a 95% confidence interval whose half-width is 5.7. If the true treatment difference is -9.0 points, the statistical power for the co-primary endpoint of DSQ will be 80% using a two-sample t-test.

Part B

The study includes two double-blind placebo-controlled randomized parts: Part A and Part B. An objective of Part A was to evaluate the Part B sample size. Part A database lock occurred on 20 May 2020 and the study results for the co-primary endpoints from Part A are below:

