- The proportion of patients achieving peak esophageal intraepithelial eosinophil count of ≤ 6 eos/hpf at 24 weeks was 5.1% in placebo group and 59.5% in dupilumab 300mg QW group with a treatment difference of 55.4%
- The mean (standard deviation [SD]) of change from baseline in DSQ total score at week 24 was -9.6 (15.2) in placebo and -21.9 (14.6) in the dupilumab 300mg QW group with a treatment group difference of -12.3.

Based on the Part A study results, the planned sample size for Part B is approximately 70 patients in each treatment group such that for the comparison of each dupilumab dose regimen to placebo:

- This sample size will yield >99.9% power to detect a treatment difference of 55.4% in the proportion of patients achieving peak esophageal intraepithelial eosinophil count of ≤ 6 eos/hpf at week 24 between placebo (5.1%) and each dupilumab treatment group (59.5%) at a 2-sided significance level of 5% using Fisher's exact test.
- This sample size will provide >99.9% power to detect a treatment difference of -12.3 points in the mean change from baseline in the total DSQ score to week 24 at a 2-sided significance level of 5% using a two-sample t-test, assuming a common SD of 15.0.

Therefore, the sample size of 70 patients/arm will provide an overall power of >99.9% ($99.9\% \times 99.9\%$) for the co-primary endpoints, assuming no negative correlation between the two endpoints. In Part B, the same treatment effect for the two 300 mg dupilumab dose regimens (ie, QW and Q2W) is assumed.

Sample size calculations were made using nQuery Advisor 7.0.

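### Part B DSQ power and overall co-primary power are 99.8% (99.3% after the stated 15% dropout) on the plan's own inputs, not above 99.9%, and 59.5% minus 5.1% is 54.4 points, not 55.4

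*SAP*

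**What the plan says.** SAP 2.3 takes its Part B assumptions from the Part A results. The mean change in DSQ total score "was -9.6 (15.2) in placebo and -21.9 (14.6) in the dupilumab 300mg QW group", a difference of -12.3 points. For histologic response, protocol 10.2 gives "5.1% in placebo group and 59.5% in dupilumab 300mg QW group with a treatment difference of 55.4" per cent, and SAP 2.3 repeats these figures.

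From these the SAP concludes for DSQ: "This sample size will provide >99.9% power to detect a treatment difference of -12.3 points", tested "at a 2-sided significance level of 5% using a two-sample t-test, assuming a common SD of 15.0", with about 70 patients per arm. For response it claims power above 99.9% with Fisher's exact test, pairing the 55.4% difference with the rates 5.1% and 59.5%.

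The two powers are then combined. The synopsis reports "an overall power of >99.9% (99.9% × 99.9" per cent in the bracket), assuming no negative correlation between the endpoints. Protocol 10.2 and SAP 2.3 carry the same statement.

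On attrition, SAP 2.3 says: "A dropout rate of 15% is assumed for the sample size calculations". Protocol 10.2 applies the same 15% to every sample size calculation in that section.

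**The concern.** Three printed figures can be tested against the inputs printed beside them: the DSQ power, the overall power and the response difference. The overall power is in doubt by inspection, because two probabilities of 99.9% multiply to less than 99.9%. The response difference fails a simple subtraction. The DSQ power needs a short calculation.

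These figures are the operating characteristics that accompany the reduction of Part B from 345 to 210 patients in protocol Amendment 5. A regulator or ethics committee that recomputes them will find that they do not reproduce as printed. What is at stake is the accuracy of the sample size justification in two documents, not the adequacy of the trial.

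**Working it through.** **Inputs.** From SAP 2.3 and protocol 10.2: DSQ difference 12.3, SD 15.0, two-sided alpha 0.05, two-sample t-test, 70 per arm, dropout 15%, response rates 5.1% and 59.5%, Fisher's exact test. Allocation is 1:1:1, so each comparison with placebo is 1:1.

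**DSQ power, 70 per arm.** Power is the probability that a noncentral t variable with 2n - 2 degrees of freedom and noncentrality δ / (SD × √(2/n)) lies beyond the critical value.

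- Standard error: 15.0 × √(2/70) = 2.535
- Noncentrality: 12.3 / 2.535 = 4.851, with 138 degrees of freedom and critical value 1.977
- Power: 99.79% (normal approximation 99.81%)

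**DSQ power after dropout.** 70 × 0.85 = 59.5 per arm.

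- At 59: standard error 15.0 × √(2/59) = 2.762, noncentrality 12.3 / 2.762 = 4.454, power 99.30%
- At 59.5: 99.33%
- At 60: 99.37%

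**Is this the plan's own dropout convention?** Part A in protocol 10.2 states 80% power for 40 per arm, difference 9.0 and SD 13.0. With 40 analysed the power is 86.4%. With 40 × 0.85 = 34 it is 80.3%. The Part A power was therefore calculated after dropout.

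**Can another reading of the inputs give more than 99.9%?** At 70 per arm, two-sided:

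| SD | Source | Power |
|---|---|---|
| 14.6 | dupilumab arm, Part A | 99.86% |
| 14.9 | pooled: √((15.2² + 14.6²)/2) | 99.81% |
| 15.0 | stated | 99.79% |
| 15.2 | placebo arm, Part A | 99.74% |

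None of these reaches 99.9%. It would take an SD of about 14.3 or less at 70 per arm, or 77 evaluable per arm at SD 15.0 (77 / 0.85 ≈ 91 randomised). Two settings outside the stated ones do reach it without dropout: a one-sided 5% test (99.93%) and SD 13.0 (99.98%). The documents do not say that either was used for Part B.

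**Histology power.** Exact enumeration of Fisher's test with 5.1% and 59.5% gives more than 99.99% at 70, 60 and 59 per arm. The plan's figure is correct. Raising the active rate to 60.5%, which would make the difference 55.4 points, leaves it above 99.99%.

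**Overall power.** Success on both endpoints cannot be more probable than success on DSQ alone, so 99.79% is a ceiling whatever the correlation. Because the histology power is almost 1, the product is practically equal to that ceiling: 99.79% at 70 per arm and about 99.3% after dropout. The printed bracket gives 0.999 × 0.999 = 0.9980, or 99.8%. Two powers each known only to exceed 99.9% guarantee a joint power above 99.8%, not above 99.9%.

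**Response difference.** 59.5 - 5.1 = 54.4 percentage points.

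**The case against.** The strongest objection is that nothing depends on this. The DSQ shortfall is about 0.1 point (99.9 - 99.79), or 0.6 point after dropout (99.9 - 99.3). No passage sets 99.9% as a target, and Amendment 5 attributes the smaller Part B to the larger DSQ effect seen in Part A. All of that stands, and it is why the point is editorial. It does not make the printed bound true.

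Second, the primary DSQ analysis is an ANCOVA adjusted for baseline and strata in all randomised patients with multiple imputation, not a t-test. Baseline adjustment would normally reduce the residual SD. The documents give no baseline-to-change correlation, so its size has to be assumed. With residual SD = 15.0 × √(1 - r²), r = 0.30 gives 99.90% at 70 per arm and 99.62% at 59, while r = 0.50 gives 99.98% and 99.92%. A reader might infer that the design delivers less power than claimed. The documents do not support that. They support only the statement that the figure is wrong for the t-test the plan names.

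Third, 55.4% may be a stratification-adjusted Part A estimate, since the planned response analysis is a Cochran-Mantel-Haenszel test across age and PPI strata. This is possible. Neither document labels it so, and the power sentence pairs it with two crude rates and an unstratified test. The objection supports offering a label as an alternative to correction.

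A reader might also take the irregular SD in the synopsis as leaving the input in doubt. Protocol 10.2 and SAP 2.3 both print 15.0, and the synopsis string may come from text extraction or an unaccepted edit, so nothing rests on it.

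**Conclusion.** The point holds as a correction of figures. Under the stated t-test, DSQ power is 99.8% at 70 per arm and 99.3% at about 59 per arm. Overall co-primary power is the same to one decimal place. The plan's bound of more than 99.9% is not met for either, and the bracket beside the overall figure equals 99.8%. The two stated response rates differ by 54.4 points, so 55.4% is either a slip or an unlabelled adjusted estimate.

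This rests on the stated inputs and on treating 15% dropout as loss of evaluable patients, which is the convention that reproduces the Part A power.

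Two stronger conclusions might be inferred, and neither is supported. The trial is not underpowered: 99.3% is ample. The histology power is not wrong either: Fisher power depends on the two rates and the arm size, all of which are stated, and it exceeds 99.99%.

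**What to change.** In the protocol synopsis, protocol 10.2 and SAP 2.3:

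- Restate DSQ power under the named t-test as 99.8% with 70 evaluable per arm and 99.3% with 15% dropout.
- Restate overall co-primary power as 99.8% and 99.3% on the same two bases, and remove or correct the bracketed product.
- Change the response difference to 54.4%. If 55.4% is the stratification-adjusted Part A estimate, label it so and do not present it as the difference between 5.1% and 59.5%.

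Leave the histology power as it is. The cost is a text correction with slightly less favourable figures. Sample size, analysis and conduct do not change.
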